7.2.4 Safety Analyses

Safety will be assessed through the number of adverse events that occur over the course of the study. Adverse event rates will be compared to that of published literature.

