2.4 Potential Risks & Benefits

2.4.1 Known Potential Risks

The application of tDCS is associated with low risks as reported by previous clinical and research studies [Bikson et al., 2016; Woods et al., 2016]. The most common side effects of tDCS are classified to be mild, benign, short-lived, and the rates of common adverse effects did not differ between the active arms of the studies and the sham arms [Bikson et al., 2016].

The most immediate safety risk for tDCS is the potential for mild irritation resulting from tingling, itching, or warmth/burning sensations during and immediately following treatments. However, risk to subject has been substantially ameliorated through the implementation of several aforementioned recommendations (included in the exclusion criteria), and standard parameters.

Standard parameters to date indicates that the current is less than 5 mA, it is applied through electrodes that are known to minimize skin burns at the specific current level (i.e. wet saline electrodes as used in this protocol), the current application duration is less than 20-60 min per session, and that the sessions are not more frequent

[figure not shown]
CONFIDENTIAL

This material is the property of the NYU School of Medicine and Langone Medical Center. Do not disclose or use except as authorized in writing by the study sponsor

Interventional Template Version: 28 APR 2017

than twice per day.

The most common adverse events (AE) of tDCS are [Brunoni et al., 2011]: itching (39.3%), tingling (22.2%), headache (14.8%), burning sensation (8.7%), and discomfort (10.4%). Based on our extensive use in previous studies a physical burn or lesion has never occurred. The following figure (Fig. 1) displays adverse events reported through our previous studies. AE rates were largely on par with those reported in the literature to date.

Risks associated with the PA program are limited to mild risks from cycling including potentially uncomfortable physical exertion and increased heartrate.

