3.2 Secondary Objectives

- To determine the feasibility of delivering at-home a structured and supervised PA program paired with tDCS
- To evaluate changes in functional mobility after tDCS and PA treatment by instrumented Time Up and Go (i-TUG) performed using wearable inertial sensors at baseline, and at 4-week.
- To evaluate change in non-motor symptoms such as general perceived fatigue, cognitive and psychological aspects
- To evaluate safety and tolerability by assessing both experiences of minor adverse events and pain ratings
- To evaluate changes in level of daily physical activity and sleep as assessed by the ActiGraph device (optional)
- To collect pilot data on tDCS-related changes in brain activity as measured by 3-electrodes frontal EEG sensor (optional)
- To evaluate changes in standing balance measures provided by static Posturography test

Study Design and Endpoints

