3.4.2 Secondary Study Endpoints

- The feasibility of delivering at-home supervised PA paired with tDCS will be assessed using the number of completed sessions at-home. It will be considered as “feasible” when participant complete successfully at least 80% of the total at-home sessions
- Comparisons between the active and sham conditions at baseline and at the end of the study by assessing the changes in gait spatial-temporal parameters (stance, swing and double support phase; cadence; step width) and functional mobility parameters objectively assessed using wearable inertial sensors
- Comparisons between the active and sham conditions at baseline and participation end conditions by assessing the changes in scores of 9-item FSS (physical aspect of fatigue) and 21-item MFIS (physical 9 items, cognitive 10 items, psychosocial 2 items), MSWS-12 (subjective measures of impact for walking ability and related pathology), and MSQOL-54 (36 items for generic health-related quality of life measures and 18 items for MS-specific measures).
- Comparisons between the active and sham conditions at baseline and participation end conditions by assessing the changes in scores of VAS- F₀₋₁₀ (to assess the perceived general fatigue)
- Review of experiences of minor adverse events and pain ratings. In particular, participants will have to report and rate any adverse events. Pain ratings will be measured, using a VAS- P₀₋₁₀ (rating 1 for minimal to 10 for most severe), before and after each session (any experience of pain or other adverse event above an intensity rating of 7 will result in study discontinuation)
- Comparisons between the active and sham conditions at pre and post tDCS-PA session by assessing the changes in the performance of the cognitive tests and EEG signal changes during the time of testing
- Comparisons between the active and sham conditions at baseline and participation end conditions by monitoring the changes in level of daily physical activity and amount of sleep as measured by ActiGraph
- Comparisons between the active and sham conditions at baseline and participation end conditions by monitoring the changes in sway parameters as objectively measured by the instrumented Posturography test and by monitoring changes in total score Berg Balance Scale.
- Change in processing speed between baseline and immediately after the treatment end to assess improvement in cognitive function as indirect effect of aerobic PA.

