4.9.2 Remotely-Supervised tDCS Sessions

Following procedures for our validated protocol ^{25, 69}, participants will receive training on the use of the study tDCS device and preconfigured laptop computer. Participants will be given a study laptop computer which will be configured with VSee⁶⁷ and TeamViewer⁶⁸. VSee is a HIPAA compliant teleconferencing video software that encrypts data before sending, creating a secure connection between two computers. TeamViewer is a HIPAA compliant program for remote access to directly provide technical support. A tDCS kit will be provided for the participant to take home which will include the tDCS device, tDCS headset, and the one-time use sponge pockets for electrodes. The Cubii will be shipped to the participant's address.

The remotely-supervised sessions will be administered by study technicians who will be connected live with participants via the study provided laptop when initiating and delivering the treatment and can address and document any safety concerns that arise during treatment. The tDCS device is pre-programmed with a single-use unlock codes that must be entered each day in order for the stimulation to begin. The code will be provided by the study technician each day after the participant meets all safety checkpoints. Study technicians will direct headset placement remotely and will observe the patient for duration of the session in real-time. The technicians

CONFIDENTIAL

are IRB approved study team members who completed CITI, HIPAA, and study-specific training in tDCS, Vsee, and Team Viewer.

If the participant wishes to discontinue the session at any time, they will be instructed to press the "abort" key, which ramps down and ceases the stimulation current within 30 seconds and afterwards permits headset removal.

At each treatment session, participants will complete brief adverse event reports before and after treatment.

Figure 1: Example of RS-tDCS equipment and setup

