5.3.3 Intermediate Remote Visits (Day 2 to Day 10)

- Administer the study treatment for 9 visits
(Active stimulation: 20 mins of tDCS (2.5mA) while participants will complete physical training; Sham stimulation: 20 mins of tDCS sham stimulation, no current delivery during the session, while participants will complete physical training)
- Record adverse events as reported by participant with pain ratings (VAS- P₁₋₁₀) and self-reporting and rating possible adverse events during each stimulation session
- Monitoring of perceived exertion using Borg scale. Borg scale will be administered by study technician every 5 minutes during the 20 minutes PA training
- Instructions provided to participants after the session: no concurrent physical therapy for the entire duration of the study
- Optional: Only for the first (day 1) and follow-up (day 11) may participants' be asked to wear EEG electrodes. While performing cognitive tests (CogState and the SDMT) before and after the stimulation period, participant's EEG signals will be simultaneously recorded for ten minutes.

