Secondary	To determine the effect of the combination of the tDCS and PA on fatigue	Physical aspect of fatigue with 9-item FSS	1. Prior to treatment beginning 2. After treatment end 3. 4 weeks follow up	No
Secondary (Optional)	To determine the effect of tDCS on brain activity during the performance of cognitive test	Change in EEG signal before and after tDCS session	1. Prior to treatment beginning and after treatment end during Day1 and Day 10 visit	No
Secondary	To determine the globally effect of the combination of the tDCS and PA	Physical, cognitive and psychosocial aspect with 21-item MFIS	1. Prior to treatment beginning 2. After treatment end 3. 4 weeks follow up	No
Secondary (Optional)	To determine the effect of tDCS treatment on level of daily physical activity and sleep	Intensity of physical activity, daily step count and number of sleeping hours	1. From baseline visit to follow-up visit	No
Secondary	To determine the effect of the combination of the tDCS and PA on walking ability	Subjective walking ability with MSWS-12	1. Prior to treatment beginning 2. After treatment end 3. 4 weeks follow up	No
Secondary	To determine the effect of the combination of the tDCS and PA on fatigue	Perceived general fatigue with VAS- F ₀₋₁₀	1. Prior to treatment beginning	No

CONFIDENTIAL

This material is the property of the NYU School of Medicine and Langone Medical Center. Do not disclose or use except as authorized in writing by the study sponsor

Interventional Template Version: 28 APR 2017

			2. After treatment end 3. 4 weeks follow up	
Secondary	To evaluate the presence of adverse events and subjective pain during stimulation	Experience of AE and pain ratings with VAS-P ₀₋₁₀	1. After treatment end	Yes
Secondary	To determine the effect of the intervention tDCS+PA on processing speed	Change from baseline in processing speed (BICAMS, Cogstate Brief Battery)	4. Baseline 5. After treatment end 6. 4 weeks follow up	No

This section should contain all pertinent documents associated with the management of the study. The following lists a few examples of potential attachments:

- Investigator Agreement (for any investigator, other than sponsor-investigator, who participates in the study)
- Sample Consent Form
- Study Procedures Flowchart/Table
- Study Monitoring Plan

CONFIDENTIAL

This material is the property of the NYU School of Medicine and Langone Medical Center. Do not disclose or use except as authorized in writing by the study sponsor

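### Pain ratings taken around every session have no specified analysis beyond generic summary statistics and no active-versus-sham comparison, and the time frame given for them in Section 15 does not fit their stated aim

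*Combined protocol and SAP*

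**What the plan says.** Section 3.2 makes pain part of a secondary objective: "To evaluate safety and tolerability by assessing both experiences of minor adverse events and pain ratings". Section 3.4.2 turns this into a secondary endpoint, worded as "Review of experiences of minor adverse events and pain ratings". It has VAS-P rated on either side of every session and ties a rating above 7 to discontinuation.

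Collection at the sessions is described consistently. Section 4.9.2 says "participants will complete brief adverse event reports before and after treatment". Section 5.3.3 asks for pain ratings together with "self-reporting and rating possible adverse events during each stimulation session". The Section 16 schedule marks VAS-P at baseline, at the stimulation sessions and at the treatment-end visit, but not at the 4-week visit.

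The only analysis headed as safety is Section 7.2.4: "Safety will be assessed through the number of adverse events that occur over the course of the study". It adds a comparison of event rates with the literature. The objectives table in Section 15 states the aim as "To evaluate the presence of adverse events and subjective pain during stimulation", but the single time frame in that row is after the end of treatment.

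**The concern.** Section 2.4.1 describes the most immediate risk of the device as "tingling, itching, or warmth/burning sensations during and immediately following treatments". An effect of that kind is short-lived and graded. It is best seen in the change from just before to just after a session, compared with the same change under sham. The trial collects this and has a concurrent sham arm, yet the stated safety method is an event count set against outside rates.

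If pain rises by a modest amount at each active session, a count may register it only in part, because it drops intensity and depends on whether a participant reports the rise as an event. A reader of the final report would then lack the most direct evidence on tolerability that the design can give. The Section 15 time frame adds doubt about which ratings are meant to answer the objective.

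**Working it through.** The plan states no figure for this point, so the check is mainly a comparison of sections.

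**1. How much data is involved.** Sessions per participant: 10 (Section 4.9.1). Ratings per session: 2 (Section 3.4.2). Enrolled: 80; evaluable: 72 (Section 4.5).
- Per participant: 10 x 2 = 20 ratings, or 10 before/after pairs.
- All enrolled: 80 x 20 = 1,600 ratings, 800 pairs.
- All evaluable: 72 x 20 = 1,440 ratings, 720 pairs.

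These are upper limits, assuming no missed sessions.

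**2. Which planned analyses could use them.**

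| Section | What it offers | Does it use the session pairs by arm? |
|---|---|---|
| 7.2.1 | Means, medians, SDs and ranges for all secondary outcomes | Covers VAS-P in general terms; names no change score, session summary or arm contrast |
| 7.2.3, questionnaire scores | RM-ANOVA with arm and three time levels: Day 1, Day 10, 4 weeks | No |
| 7.2.4 | Number of adverse events; rates against the literature | No; pain ratings and sham are not mentioned |

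The RM-ANOVA route rests on Section 5.2, which lists VAS-P among the self-administered questionnaires. It fails for three reasons. The visit questionnaire lists in 5.3.2, 5.3.4 and 5.3.5 name the fatigue scale but not VAS-P. VAS-P is not scheduled at 4 weeks, the third time level. With one value on Day 1 and one on Day 10, the model would take at most 2 of the 20 session ratings and no within-session difference.

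**3. The Section 15 time frame.** The pain row aims at pain during stimulation but is timed after the end of treatment. Sections 3.4.2, 5.3.3 and 16 place the ratings at the sessions. Two rows of the same table show that the label can be read in other ways. The at-home session count has the same time frame although it accumulates over the course. The EEG row uses similar words for the end of a session, but adds Day 1 and Day 10; the pain row has no such qualifier.

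**4. The scale label.** Sections 5.2, 15 and 16 give 0-10, Section 5.3.3 gives 1-10, and Section 3.4.2 carries a 0-10 label with a description starting at 1.

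**5. What averaging over sessions could add (illustration only).** The documents give no SD or correlation for VAS-P. Assume an SD of 2 points for the within-session change and 36 per arm (72 / 2), with ICC the correlation between a participant's sessions.
- One session: SE = SD x sqrt(2/36) = 2 x 0.2357 = 0.47.
- Mean of 10 sessions: SE = SD x sqrt((ICC + (1 - ICC)/10) x 2/36).
- ICC 0.2: 2 x sqrt(0.28 x 2/36) = 0.25. ICC 0.4: 2 x sqrt(0.46 x 2/36) = 0.32. ICC 0.6: 2 x sqrt(0.64 x 2/36) = 0.38.
- Power for an assumed 1-point excess = 1 - Phi(1.96 - 1/SE): 56% from one session; 98%, 88% and 76% from ten.

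Over SD 1.5 to 2.5 and ICC 0.2 to 0.6, the ten-session power runs from 56% to nearly 100%. The finding does not depend on these figures.

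**The case against.** The strongest reply is that pain is not ignored, and much of it stands.

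- **A reader might infer that the ratings enter no analysis.** That goes too far. Section 7.2.1 plans summary statistics for every secondary outcome, and Section 3.4.2 uses the ratings in managing individual participants.
- **A reader might infer that session pain would go unreported.** The documents do not support this. Section 6.1.1 counts any symptom that appears or gets worse as an adverse event, reports are taken around every session (4.9.2, 5.3.3), and event rates are calculated and reviewed (6.4.1). Tingling, itching and burning would be captured in this way.
- **A reader might infer that Section 15 moves the measurement to a time when session pain has gone.** It more plausibly names when the accumulated data are evaluated. Three other sections place the ratings at the sessions, so this is a label to clarify.
- **A reader might infer that background MS pain biases the comparison.** Randomisation makes it noise rather than bias between arms, and Section 6.3 excludes conditions present at screening unless they deteriorate. Nor does the before-to-after change alone isolate stimulation, since both arms also cycle for 20 minutes; only its contrast with sham does.

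It can also be said that a pilot needs no formal model for tolerability and that a by-arm table would do. That is fair as to the choice of model. It does not answer the absence of any specified by-arm pain summary.

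**Conclusion.** The point holds in a limited form. A named secondary safety endpoint, rated up to 20 times per participant, has no specified analysis beyond generic descriptive statistics. Section 7.2.4 does not use it, the questionnaire model cannot use its pairs, and no active-versus-sham comparison of pain is planned. What would be lost is the graded comparison with sham; pain reported as an adverse event would still be seen.

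This rests on reading the sections together, not on a calculation. The count of 1,600 ratings assumes full attendance, and the precision and power figures rest on assumed SDs, correlations and effect size. The matter does not touch the primary endpoint. It is worth correcting because it is a concrete gain in the tolerability evidence at almost no cost.

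**What to change.** Add to Section 7.2.4, in words such as: *The after-minus-before change in VAS-P at each of the 10 sessions will be summarised by arm. The active-sham mean difference over sessions will be given with a 95% confidence interval, for example from a mixed model with a random participant effect, session and pre-session rating. Each participant's maximum increase will be tabulated by arm. All sessions completed before any discontinuation will be included.*

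The last sentence matters because a high rating can end participation, and Section 5.3.6 lists no assessments at early termination; participants with the most pain could otherwise drop out of the summary. From session 2 on, the pre-session rating is measured after randomisation, so the simple by-arm mean changes should stand beside any adjusted estimate.

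Reconcile the Section 15 time frame for this row with Sections 3.4.2, 5.3.3 and 16, and use one VAS-P scale label throughout.

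Keep the existing adverse event definition. A rule that counts an event only when it is new or worse straight after a session should not be added: it could miss delayed effects, such as a headache first noted at the next pre-session report.

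The cost is a short change to the analysis text, one table correction and one added safety table. No new data, visits or clinical rules are needed.

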2.2.1 Clinical Data to Date

To the best of our knowledge, there is no available clinical research data on the effects of the combination of tDCS and simultaneously performed PA in pwMS. However, PA has been proposed as a useful and effective approach to improving some of the most typical motor impairments caused by MS [Motl et al., 2005; Motl, 2010].

The most promising results, published for the improvement of motor performances, are on hand dexterity wherein tDCS was applied alone or in association with motor training [Iodice et al., 2017]. There is positive outcome data from other clinical trials conducted in patients with neurologic diseases with impaired mobility including modulation of cortical excitability and enhanced motor skill learning, locomotion, and balance [Iodice et al., 2017, Kaski et al., 2013, Pozzi et al., 2014].

Our lab has conducted multiple tDCS trials to date, with two active IRB protocols through NYU Langone Health. We have conducted over 2000 sessions of tDCS paired with cognitive remediation with extremely high tolerability and feasibility (>99%). We have positive clinical outcomes with statistically significant improvement of cognitive processes and reduction in fatigue in pwMS.

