2.4.2 Known Potential Benefits

Previous research on the use of tDCS in pwMS reported a range of immediate potential benefits such as:

- Improvement in cognitive functioning and working memory [Charvet et al., 2017]
- Reduction in depression symptoms and fatigue [Ferrucci et al., 2014; Saiote et al., 2014; Charvet et al., 2017]
- Reduction in pain and anxiety [Mori et al., 2010]

The long-term potential benefits of repeated applications of tDCS, their interaction with specific learning stages and tasks and the extent to which these performance improvements are retained in the long term remain to be addressed.

CONFIDENTIAL

This material is the property of the NYU School of Medicine and Langone Medical Center. Do not disclose or use except as authorized in writing by the study sponsor
Interventional Template Version: 28 APR 2017

The use of our established RS-tDCS protocol can improve access to physical activity programs, increase the engagement and remove the barriers of time and travel to clinic appointments (Shaw et al., 2019; Charvet et al., 2020).

3 Objectives and Purpose

In pwMS comparing those receiving active stimulation versus those receiving sham stimulation, the objectives are as follows:

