3.3 Description of Study Design

This is an interventional, randomized, double-blind (participant and study staff), sham-controlled, parallel design, pilot study of N=80 RR-MS and SP-MS participants, characterized by mild to moderate gait dysfunctions. There will be a 1:1 random assignment of participants to receive either the active or the sham tDCS while performing the PA program. Blocked stratification will be used to randomize the participants to their respective study conditions. Block sizes of 4 and 6 will be used and the stratifying factor will be EDSS score (0-3.5 and 4.0-6.5). Randomization will be done by an independent randomizer who takes no part in baseline, follow-up, or sessions to maintain the double-blind nature of the study.

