7.1 Statistical Hypotheses

Research hypothesis

There is a significant difference between active and sham groups by comparing primary and secondary outcomes at baseline and end treatment time.

Null hypothesis

There will not be a significant difference between active and sham groups

CONFIDENTIAL

This material is the property of the NYU School of Medicine and Langone Medical Center. Do not disclose or use except as authorized in writing by the study sponsor

Interventional Template Version: 28 APR 2017

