7.2 Description of Statistical Methods

7.2.1 General Approach

Study design of the study is a double- blind randomized controlled trial.

The primary, secondary outcomes and demographic variables will be examined with summary statistics, including means, medians, standard deviations (SD), minimum, and maximum values for continuous variables, and frequencies and proportions for categorical variables.

The characteristics of the participants in the two groups will be compared at baseline using two- sample t-tests for continuous variables and the chi-square test for categorical variables.

The Shapiro-Wilk test will be performed, histograms will be constructed, and measures of central tendency and dispersion will be calculated to test the assumption that distribution is normal. If the normality check will fail, a transformation of the data will be done as corrective procedures.

The general approach of statistical analyses will be a repeated-measures analysis of variance (RM-ANOVA) with tDCS (2 levels: Active and Sham) as the between-independent variable and Time (3 levels: Day 1, Day 10, and after 4-weeks) as the within-independent variable.

In the inferential tests statistical significance will be set at 5% and all p-values is two-sided.

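### Section 7.2.4 compares adverse event rates only with published literature, so the randomised sham arm yields no specified estimate of the adverse event excess under active current

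*Combined protocol and SAP*

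**What the plan says.** Section 7.2.4 is two sentences long. The first bases safety on the number of AEs during the study. The second gives the comparison: "Adverse event rates will be compared to that of published literature". It does not say whether rates are pooled or split by arm, or whether they are per participant or per session.

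The rest of the plan is built on the randomised contrast:

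- Section 3 opens its list of objectives with "In pwMS comparing those receiving active stimulation versus those receiving sham stimulation, the objectives are as follows".
- Section 3.2 includes among them "To evaluate safety and tolerability by assessing both experiences of minor adverse events and pain ratings".
- Section 3.3: "There will be a 1:1 random assignment of participants to receive either the active or the sham tDCS while performing the PA program".
- Section 3.4.2 lists as a secondary endpoint "Review of experiences of minor adverse events and pain ratings", with pain (VAS-P) rated before and after each session.
- Section 7.1 states the research hypothesis as "There is a significant difference between active and sham groups by comparing primary and secondary outcomes at baseline and end treatment time".
- Section 7.2.1 promises summary statistics for the outcomes, including "frequencies and proportions for categorical variables", without mentioning AEs or saying that summaries are by arm.

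**The concern.** The trial randomises participants to a sham control that shares the population, the exercise programme and the method of AE collection. For the question of what active current adds, that arm is the natural reference. The one safety comparison the plan specifies is instead with outside studies, which may differ in all three respects.

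Followed as written, the plan would give no estimate of the AE excess of active over sham, although the safety objective sits under an active-versus-sham heading. There is a second hazard. Since 7.2.4 does not say that rates are taken by arm, a rate pooled over active and sham could match the literature while the active arm carried a clear excess.

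**Working it through.** **Step 1. Search for a between-arm AE analysis.** The plan states no figure for the AE comparison, so there is none to reproduce. The relevant sections, side by side:

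| Section | What it gives for AEs |
|---|---|
| 3.4.2 | A review; most neighbouring endpoints are worded as active-sham comparisons |
| 6 (introduction) | Monitoring meetings review AE rates; no arm split stated |
| 6.4.1 | Literature rates serve as the trigger for a study hold |
| 7.1 | Generic active-sham hypothesis on secondary outcomes; no AE method |
| 7.2.1 | Generic summaries and repeated-measures ANOVA; AEs not named |
| 7.2.3 | Between-arm ANOVA for Timed Up and Go, sway and questionnaire scores only |
| 7.2.4 | AE count, compared with literature |
| 15 (objectives table) | Presence of AEs and pain; no comparison stated |

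The contrast in 7.1, at baseline and end of treatment, also fits poorly with events that occur during treatment.

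**Step 2. Could a literature comparison miss an excess?** Illustration with assumed rates. Section 2.4.1 quotes itching at 39.3%. With 1:1 allocation, suppose sham 25.0% and active 53.6%:

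- pooled rate = (25.0 + 53.6)/2 = 39.3%, exactly the literature figure
- arm difference = 53.6 − 25.0 = 28.6 points

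A pooled comparison would show no excess. A two-sided 5% test between arms of 36 would have about 71% power for that gap. This masking arises only if rates are pooled, which 7.2.4 leaves open.

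**Step 3. What precision would a by-arm comparison have?**

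Inputs:

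- 80 participants randomised 1:1 (3.3), so 80/2 = 40 per arm.
- 10% dropout leaves 72 (4.5), so 72/2 = 36 per arm as a lower case.
- AE rates from 2.4.1. That section gives no denominator, so I assume they are per participant and equal in both arms.

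Formulas, with *l* and *u* the 95% Wilson limits for one arm at rate *p*:

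- Newcombe half-width (equal rates and arm sizes) = √[(p − l)² + (u − p)²]
- Wald half-width = 1.96 × √[2p(1 − p)/n]

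Example, burning at n = 40: l = 0.0323, u = 0.2141. Newcombe = √(0.0547² + 0.1271²) = 0.138. Wald = 1.96 × √(2 × 0.087 × 0.913/40) = 0.124.

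| AE (rate) | Newcombe, n = 40 | Wald, n = 40 | Newcombe, n = 36 |
|---|---|---|---|
| Itching (39.3%) | 20.5 | 21.4 | 21.5 |
| Tingling (22.2%) | 18.1 | 18.2 | 19.0 |
| Headache (14.8%) | 16.1 | 15.6 | 17.0 |
| Discomfort (10.4%) | 14.5 | 13.4 | 15.4 |
| Burning (8.7%) | 13.8 | 12.4 | 14.7 |

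Half-widths are in percentage points. Burning implies 0.087 × 40 ≈ 3.5 participants per arm with the event. At such counts the Wald interval is too narrow, which is why I use Newcombe.

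**The case against.** **The intent is already there.** Section 7.1 covers secondary outcomes, AEs are listed among them, and 7.2.1 promises frequencies and proportions. A reader might infer from 7.2.4 that the plan abandons the active-sham question for safety. The documents do not support that: the intent is stated, and what is missing is an AE analysis that carries it out.

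**A descriptive review may be deliberate.** This is a pilot, 3.4.2 speaks of a review, and the literature benchmark matches the hold trigger in 6.4.1, which does not need arm-level data. This explains the choice and is fair for monitoring. It does not supply a final summary by arm, and a descriptive summary can itself be by arm.

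**The literature still has a use.** Section 2.2.1 says "there is no available clinical research data on the effects of the combination of tDCS and simultaneously performed PA in pwMS". A reader might infer that published rates are therefore worthless here. That goes too far: the sentence concerns effects of the combination, and published rates can still benchmark the sensations of stimulation itself. Sham has its own limits. Its current ramps are expected to be felt (2.3, 4.9.1), so the arm difference may understate absolute sensation rates, and it cannot isolate AEs of exercise, which both arms receive.

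**Two further inferences to resist.**

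- One might argue that VAS-P cannot fill the three time levels of the questionnaire ANOVA, because section 16 schedules none at 4 weeks. The plan never assigns VAS-P to that ANOVA. Sections 5.3.2 and 5.3.4 leave it out of the visit questionnaires, and 3.4.2 takes it around each session.
- One might argue that unblinding at the participation end visit (7.4.3) spoils an arm comparison of AEs. The common effects are described as short-lived (2.4.1) and reports are taken at each session (4.9.2), so this is peripheral.

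**Unseen sources.** The stop-criteria document (4.6.1) and the site monitoring plan (6.6) are not among the documents reviewed, and part of section 5 was removed. The search covers the visible text only.

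**Conclusion.** The point stands: published literature is the only comparator 7.2.4 names for AE rates, and nothing visible specifies a between-arm AE analysis, although safety is an active-versus-sham objective. The primary efficacy analysis is unaffected. The plan should be changed because the safety conclusion would otherwise rest on an external benchmark while a concurrent randomised control goes unused.

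The gain is limited. Half-widths run from about 14 to 21 points at 40 per arm and 15 to 22 at 36, assuming that the 2.4.1 rates apply per participant and equally in both arms. These intervals would reveal only large differences.

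**What to change.** In 7.2.4, for participants treated at least once:

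1. Report by arm the number and proportion of participants with each AE.
2. Give the active-minus-sham risk difference with a 95% Newcombe interval, labelled as estimation and not a powered test.
3. Summarise the pre- to post-session VAS-P change by arm.
4. Keep the literature comparison alongside, with a note that the sham ramps may cause sensations and that both arms exercise.
5. State that a wide interval is not evidence of no difference.

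The cost is a few extra tables. AE reports and pain ratings are already taken before and after each session (3.4.2, 4.9.2), so no visit or procedure is added. The risk is over-reading of imprecise intervals, which items 2 and 5 address.
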